#### **8.1.1. $\text{PaO}_2/\text{FiO}_2$ ratio**

$\text{PaO}_2/\text{FiO}_2$  ratio will be evaluated by blood gas analyzer at screening for eligibility determination, within 30 minutes before dosing on Day 1 as baseline, and within 30 minutes after 2nd dose on Day 7 and Day 14. Change from baseline to Day 7 and to Day 14 on  $\text{PaO}_2/\text{FiO}_2$  ratio will be one of the secondary efficacy measures in this study.

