#### **8.3.1. Inflammatory Biomarkers**

##### **8.3.1.1. [REDACTED]**

As a proinflammatory biomarker [REDACTED] significantly elevated in COVID-19 patients and is associated with disease severity and progression. Thus [REDACTED] a reliable indicator of hyperinflammatory state.

[REDACTED] will be measured daily at local laboratories with validated methods. Change from baseline to Day 7, time (days) and number of the patients to reach 50% reduction from Baseline in [REDACTED] during the treatment period (Baseline to Day 14), and changes in daily plasma [REDACTED] during the treatment period (Baseline to Days 1-14) will be analyzed.

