Informed consent	X									
Medical history	X									
Demographics	X									
Physical examinations	X ⁴								X	
Vital signs ⁵	X	X	X	X	X	X	X	X		X

12-lead ECG	X	X ⁶		X		X		X	X
Blood samples for routine lab tests including CRP and ferritin ⁷	X	X	X	X	X	X	X	X	X
Blood samples for coagulopathy and cardiac panels ⁸		X	X	X		X		X	X
Urine sample for urinalysis	X	X	X	X		X		X	X
Serum serology and pregnancy tests for screening	X								
Inclusion and exclusion	X								
Randomization		X							
Treatment		X	X	X	X	X	X	X	
Oxygen use and saturation (pulse oximetry)	X	X	X	X	X	X	X	X	X
PaO ₂ /FiO ₂ ratio	X	X		X				X	
WHO ordinal scale		X		X				X ¹³	X
Blood sample for cytokine/chemokine panels and CV biomarkers ⁹		X		X				X	
Blood sample for PK analysis and pRIP1/pMLKL assay ¹⁰		X		X				X	
Urine sample for NGAL and KM-1 assay ¹¹		X		X				X	
AE and ConMed	X	X	X	X	X	X	X	X	X

1. Enrollment and Baseline. Screening and Baseline visits can be combined. ECG, laboratory test and other test results taken within 24 hours prior to consent will be used as Baselines.
2. End of Treatment (EOT) or early discharge.
3. End of the study (EOS) or early discontinuation.
4. For enrolled patients, physical examination obtained at screening will be the Baseline. Weight and height will be measured at screening.
5. Vital signs will be taken before the 1st dose on Day 1 as Baseline, and within 3 hours before the 2nd dose on other days.
6. Three ECGs with 1-3 min interval before the 1st dose on Day 1 only, and the means of the 3 ECGs will be used as Baselines. ECGs will be done within 3 hours before the 2nd dose on other days. Local ECG machine will be used in this study.
7. Routine laboratory tests before the 2nd dose will be done daily at local labs. CRP and ferritin tests will be done on Days 1, 3, 7, 10 and 14.
8. Coagulopathy panel including D-dimer, fibrinogen, PT, PTT and INR, and cardiac function panel including NT-proBNP (or BNP) and high-sensitivity cardiac troponin will be done on Days 1, 3, 7, 10 and 14 at local labs with samples collected before the 2nd dose.
9. One blood sample collected before the 1st dose on Day 1 and before the 2nd dose on Days 7 and 14 for cytokine/chemokine panels and CV biomarker assays to be conducted at a central lab

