13.1.1 PaO₂/FiO₂ ratio

The PaO₂/FiO₂ ratio, change and percentage change from Baseline in PaO₂/FiO₂ ratio will be summarized by visit and treatment using both simple descriptive statistics and model-based estimates. A non-parametric Wilcoxon Rank Sum test will be used to compare the treatment groups with respect to the percentage change from baseline values at Day 7 and Day 14/EOT.

A separate summary table will be produced, similar to what is described above, summarizing the results at Day 7 (assessments taking place on study day 7) and Day 14 (assessments taking place on study day 14). For any patients with missing Day 7 results, the Day 7 results will be imputed using the last value reported prior to study day 7. Similarly, Day 14 missing observations will be imputed with the last available assessment that took place after study day 7 and prior to study day 14. A summary table will be produced, summarizing these (imputed and reported) results.

The change from Baseline at each visit will be compared between treatment groups using an ANCOVA model with fixed effects for treatment and the Baseline score as a continuous covariate. Comparison of the SIR1-365 dose and placebo will be constructed based on least-squares means (LSMean) from the model.

The mean change and mean percentage change from Baseline up to Day 14, using the actual study day for Day14/EOT assessments, will be plotted per treatment group using line graphs.

As a sensitivity analysis, to assess the impact of missing data, if more than 10% of patients in either arm has a missing Day 7 PaO₂/FiO₂ ratio, a MMRM analysis will be performed. The PaO₂/FiO₂ ratio will be analyzed by a MMRM with treatment group, Day (Days 2 to 14), and treatment group-by-Day interaction as fixed factors, and the Baseline score as a continuous covariate. Day will be used as the repeated measure using an unstructured covariance structure. For both treatment groups, at Day 7, the geometric LS mean in the PaO₂/FiO₂ ratio and corresponding 95% CI will be presented. The output will also include the estimated geometric LS mean ratio for SIR1-365 dose and placebo, the corresponding 95% CI and corresponding two-sided P-value for the ratio.

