14.1.1 CRP Levels

Plasma CRP level will be measured on days 1, 3, 7, 10 and 14 at local laboratories.

Descriptive tabulation:

A descriptive summary tabulation will be provided displaying descriptive statistics of the CRP levels, changes and percentage changes from Baseline for each treatment group by visit. The mean change and mean percentage change from Baseline up to Day 14, using the actual study day for Day14/EOT assessments, will be plotted per treatment group using line graphs.

A separate summary table will be produced, similar to what is described above, summarizing the results at Day 7 (assessments taking place on study day 7) and Day 14 (assessments taking place on study day 14). For any patients with missing Day 7 results, the Day 7 results will be imputed using the last value reported prior to study day 7. Similarly, Day 14 missing observations will be imputed with the last available assessment that took place after study day 7 and prior to study day 14. A summary table will be produced, summarizing these (imputed and reported) results.

Inferential analysis:

Inferential analyses will be conducted to compare the difference in CRP levels between SIR-365 dose and placebo.

The CRP levels on Day 7 and Day 14 will be analyzed by an ANCOVA with treatment group as a fixed factor, and the respective Baseline score as a covariate in the model.

The CRP values will be log-transformed (natural log) for analysis. Comparison of the SIR1-365 dose vs placebo will be constructed based on least-squares means from the model. The results will be back transformed for presentation including 95% CI constructed for both within and between treatment estimates.

For both treatment groups the number of observations, the geometric least square mean (LS mean) in plasma CRP levels and corresponding 95% CI will be presented. The output will also include the estimated geometric LS mean ratio for SIR1-365 dose and placebo, the corresponding 95% CI and corresponding two-sided P-value for the difference.

If the residuals are found to deviate substantially from normality a supportive analysis using the non-parametric Wilcoxon Rank Sum test will be performed.

A non-parametric Wilcoxon Rank Sum test will be used to compare the treatment groups with respect to the percentage change from baseline values at Day 7 and Day 14/EOT.

Sensitivity analysis:

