As a sensitivity analysis, to assess the impact of missing data, if more than 10% of patients in either arm has missing Day 7 CRP values, a MMRM analysis will be performed. The plasma CRP levels will be analyzed by a MMRM with treatment group, Day (Days 2 to 14), and treatment group-by-Day interaction as fixed factors, and the Baseline score as a continuous covariate. Day will be used as the repeated measure using an unstructured covariance structure. For both treatment groups, at Day 7, the geometric LS mean in plasma CRP levels and corresponding 95% CI will be presented. The output will also include the estimated geometric LS mean ratio for SIR1-365 dose and placebo, the corresponding 95% CI and corresponding two-sided P-value for the ratio.

Additionally, the primary analysis for plasma CRP level on Day 7 and Day 14 will be repeated for PP set with no missing data imputation.

A separate summary table will be produced, similar to what is described above, summarizing the results at Day 7 (assessments taking place on study day 7) and Day 14 (assessments taking place on study day 14). For any patients with missing Day 7 results, the Day 7 results will be imputed using the last value reported prior to study day 7. Similarly, Day 14 missing observations will be imputed with the last available assessment that took place after study day 7 and prior to study day 14. A summary table will be produced on the PP set, summarizing these (imputed and reported) results.

Time to 50% reduction:

Time (days) to 50% reduction from Baseline in plasma CRP level during the treatment period will be analyzed using a Cox proportional hazards model to estimate the hazard ratio and corresponding 95% CI for SIR1-365 dose vs placebo.

The proportional hazard regression model will include treatment as a fixed effect.

- Patients without a 50% reduction will be censored at the date of their last CRP assessment.
- Patients with no post-baseline CRP value will be censored at Day 1.
- Death, prior to 50% reduction, will be handled as a competing risk event.

The hazard ratio estimation of the event of interest will be derived from a cumulative incidence function. The number and percentage of patients to reach 50% reduction from Baseline in plasma CRP level from Baseline to Day 14 will also be summarized. This analysis will be performed in the ITT set.

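### The conditional MMRM asks for geometric means of PaO2/FiO2 from a model with no log step, and its Days 2 to 14 factor does not match the visit schedule for PaO2/FiO2 or CRP

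*SAP*

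**What the plan says.** **The model.** SAP 13.1.1 (PaO2/FiO2) and SAP 14.1.1 (CRP) contain nearly the same sensitivity analysis. It runs when over 10% of Day 7 values are missing in one of the arms. The fixed part is "treatment group, Day (Days 2 to 14), and treatment group-by-Day interaction as fixed factors", plus baseline as a covariate. For the covariance, "Day will be used as the repeated measure using an unstructured covariance structure".

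**The output.** For PaO2/FiO2, as for CRP, geometric LS means at Day 7 are requested, and "The output will also include the estimated geometric LS mean ratio for SIR1-365 dose and placebo". A natural-log transformation is stated for CRP in 14.1.1. None is stated for PaO2/FiO2, whose main analysis in 13.1.1 is an ANCOVA of change from baseline.

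**The schedule.** After baseline, PaO2/FiO2 is scheduled on Days 7 and 14 only (protocol 8.1.1; SAP Table 5.2). For CRP, the footnote to SAP Table 5.2 says "CRP and ferritin tests will be done on Days 1, 3, 7, 10 and 14", and SAP 14.1.1 agrees: "Plasma CRP level will be measured on days 1, 3, 7, 10 and 14 at local laboratories". Protocol 8.3.1.1 instead says that its marker "will be measured daily at local laboratories with validated methods". The marker's name is blacked out there, but the protocol's table of contents titles that section as CRP levels.

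**Early discharge.** SAP 8.4 places early-discharge assessments at Day 14/EOT for every summary and statistical analysis.

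**The concern.** A sensitivity analysis for missing data is useful only if its result can be put next to the main estimate. Here the main PaO2/FiO2 result is a difference in mean change, while the sensitivity result is to be a ratio of geometric means. If the two disagree, a reader cannot tell whether the missing values or the change of scale is responsible. The programmer would also have to add a log step that the SAP does not mention, or change the output.

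The Day factor raises a separate question. Read literally, Days 2 to 14 is 13 levels, most of which have no scheduled measurement for either endpoint. Whoever fits the model must decide which days count and where a value taken at early discharge belongs. SAP section 8 treats analyses not specified before unblinding as post hoc, so these decisions should be in the SAP beforehand.

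**Working it through.** The documents give no power, effect size or SD for these endpoints, so there is no figure of the plan's own to reproduce. The check counts what the model asks for against what the schedule supplies.

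**1. Scale.**
- Main PaO2/FiO2 analysis: ANCOVA on untransformed change, giving an LS mean difference.
- MMRM: the response is the ratio itself, with no log step, so its LS means are arithmetic and its contrast is also a difference.
- With baseline as a covariate, modelling the level or the change gives the same treatment difference. That part is harmless.
- A geometric mean ratio needs a logged response. No coding of Day supplies one.

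The size of the gap needs an assumption from outside the documents. For a log-normal variable, geometric mean / arithmetic mean = 1/√(1 + CV²):
- CV 0.3: 1/√1.09 = 0.96
- CV 0.5: 1/√1.25 = 0.89
- CV 0.7: 1/√1.49 = 0.82

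**2. Day factor, nominal visits.** Inputs: Days 2 to 14 (SAP 13.1.1 and 14.1.1), the visit days given above, and about 60 patients (SAP section 6). For k day levels, the unstructured matrix has k(k+1)/2 parameters, of which k(k−1)/2 are covariances. The fixed part has 2k + 1 terms (treatment-by-day cells plus baseline).

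| | Literal, Days 2 to 14 | PaO2/FiO2, Days 7, 14 | CRP, Days 3, 7, 10, 14 |
|---|---|---|---|
| k | 13 | 2 | 4 |
| Covariance parameters | 13×14/2 = 91 | 2×3/2 = 3 | 4×5/2 = 10 |
| Of which covariances | 78 | 1 | 6 |
| Fixed effects | 27 | 5 | 9 |
| Most observations, 60 patients | – | 120 | 240 |

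Filling only the scheduled days of the 13-day grid gives a fixed-effects design of rank 5 (PaO2/FiO2) or 9 (CRP) out of 27. Software that keeps only the observed levels fits the 2-visit or 4-visit model.

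**3. Day factor, actual discharge days.** If the end-of-treatment value sits on the day it was taken, count the day pairs that one patient can supply:
- PaO2/FiO2: Day 7 with one of Days 8 to 14 = 7 of 78 pairs.
- CRP: Day 3 with Days 4 to 14 (11), Day 7 with Days 8 to 14 (7), Day 10 with Days 11 to 14 (4) = 22 of 78 pairs.

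Most covariances then have no data behind them, and a 13-day unstructured matrix cannot be estimated. The Day 14 window of ±2 days would also put some values on Days 15 and 16, outside the factor.

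**4. Early discharge under SAP 8.4.** A patient discharged on Day 5 has no Day 7 value. The Day 5 measurement enters as Day 14 and, through the Day 7–Day 14 covariance, informs the Day 7 estimate as if it came from a later time.

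**5. Trigger.** 10% of 30 is 3, so 4 or more missing in an arm of 30 starts the MMRM. Arms are only approximately 30, and the CRP analysis uses the mITT set.

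**The case against.** The strongest reply is that the wording is loose but workable. SAP 8.4 governs all statistical analyses. Where the SAP wants actual study days, as in the line plots and the last-value-carried-forward tables, it says so, and the MMRM text does not. Days 2 to 14 can be read as the post-baseline window, within which only scheduled visits hold data. This stands, and it limits the second part of the point.

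A reader might infer that the model must carry 91 covariance parameters and will fail to converge. The documents do not support that: it requires discharge values on actual days, contrary to SAP 8.4. A reader might also infer that Days 2 to 14 is left over from daily testing. The amendment log records a move from daily to five-day testing for CRP and ferritin, but that cannot explain the same wording for PaO2/FiO2.

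Nor is the MMRM the only handling of missing values. The SAP has last-value-carried-forward tables for both endpoints and a saturation-derived substitute for missing PaO2/FiO2 (13.1.1.1). Protocol 10.3.3 also allowed multiple imputation for the inflammatory marker. These are not equivalent to the MMRM, but they lower the stakes. The documents give no discharge rate, so how likely the trigger is cannot be stated.

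On scale, one can argue that geometric output implies a log step. If so, the step is unstated, and the ANCOVA it is meant to support remains untransformed. The mismatch is not answered.

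**Conclusion.** The analysis is wrong as written in one respect and imprecise in another.

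- **PaO2/FiO2 scale.** The requested geometric output does not follow from the stated model and is not directly comparable with the main ANCOVA. This holds under every coding of Day and needs no assumption. CRP is not affected.
- **Day factor.** It names 13 days where the schedule supplies 2 or 4. Under SAP 8.4 this is a specification error that can be fitted around. It becomes inestimable only with actual-day coding. The treatment of discharges before Day 7 needs an explicit statement under either coding.

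The reach is limited to a conditional sensitivity analysis of secondary endpoints in a study not powered for them. The primary safety analysis and the main ANCOVAs do not depend on it. The conflict over CRP frequency between protocol 8.3.1.1 and the schedule is real if the blacked-out marker is CRP, as the table of contents indicates.

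**What to change.** Before unblinding, amend SAP 13.1.1 and 14.1.1:

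1. For PaO2/FiO2, report the MMRM as an LS mean difference in change from baseline with its 95% CI, matching the ANCOVA. Alternatively, log-transform in both models and report ratios from both.
2. Define the repeated factor as the scheduled visits: Days 7 and 14 for PaO2/FiO2; Days 3, 7, 10 and 14 for log CRP.
3. State how early-discharge values enter the MMRM, in particular those taken before Day 7, which SAP 8.4 would label Day 14.
4. Reconcile the testing frequency in protocol 8.3.1.1 with the five-day CRP schedule.

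A baseline-by-visit term and a fallback covariance structure are sensible refinements but optional. The cost is a few sentences in the SAP and one correction to the protocol text. No data collection or sample size changes.

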13.1.1.1 Derived PaO₂/FiO₂ ratio

The PaO₂/FiO₂ ratio will also be derived based on the Collected O₂Sat Level (%) and the Fraction of Inspired Oxygen (FiO₂) from the O₂ Saturation Readings CRF page, and the Fraction of Inspired Oxygen (FiO₂) from the PaO₂/FiO₂ ratio CRF page.

First, the estimated PaO₂ will be calculated based on the collected O₂Sat Level and the table below.

Table 13.1.1.1

SO ₂ (%)	PaO ₂ (mmHg)
80	44
81	45
82	46
83	47
84	49
85	50
86	52
87	53
88	55
89	57
90	60
91	62
92	65
93	69
94	73
95	79
96	86
97	96
98	112
99	145
100	145

The derived PaO₂/FiO₂ ratio is calculated as follows:

Derived PaO₂/FiO₂ ratio = (Estimated PaO₂ / Collected FiO₂) x 100

If the FiO₂ is available from the PaO₂/FiO₂ ratio CRF page, then this will be used for the collected FiO₂ in the calculation above. Otherwise, the FiO₂ from the O₂ Saturation Readings CRF page will be used as the collected FiO₂ in the calculation.

For the analysis, the derived $\text{PaO}_2/\text{FiO}_2$ ratio will be used for imputation, if the collected $\text{PaO}_2/\text{FiO}_2$ ratio is missing. These collected and imputed values for the $\text{PaO}_2/\text{FiO}_2$ ratio, as well as the change and percentage change from Baseline, will be summarized by visit and treatment using both simple descriptive statistics and model-based estimates. A non-parametric Wilcoxon Rank Sum test will be used to compare the treatment groups with respect to the percentage change from baseline values at Day 7 and Day 14/EOT.

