13.1.2 Time to improvement of oxygenation

Oxygen saturation will be measured daily via pulse oximetry.

Time to improvement of oxygenation (in days) is defined as oxygen saturation (pulse oximetry) $>93\%$ and increased by $\geq 1\%$ from Baseline breathing only room air in the 48 hours preceding the measurement.

The time to improvement will be analyzed using a Cox proportional hazards model to estimate the hazard ratio and corresponding 95% CI for SIR1-365 dose vs placebo.

The proportional hazard regression model will include a single term for treatment. Patients without a pulse oximetry $>93\%$ with an increase $\geq 1\%$ from Baseline will be censored at the date of their last pulse oximetry measurement (meeting the preceding 48 hours room air only requirement) or the last date that supplemental oxygen was received, whichever come later.

- Patients without a post-baseline oximetry measurement who did not receive supplemental oxygen will be censored at day 1.
- Death prior to an improvement will be handled as a competing risk event.

The hazard ratio estimation of the event of interest (improvement of oxygenation) will be derived from a cumulative incidence function.

Kaplan Meier curves of time to improvement of oxygenation will be plotted for each treatment group on the same graph.

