13.1.6 Patients with respiratory failure

Respiratory failure is defined as need for mechanical ventilation, ECMO, noninvasive ventilation, or high-flow nasal cannula oxygen delivery (heated, humidified, oxygen delivered via reinforced nasal cannula at flow rates >20 L/min with fraction of delivered oxygen ≥ 0.5). Other oxygen requirements recorded in the “Other, Specify” field of the eCRF

will be reviewed for any other criteria that may qualify. Any such cases will be identified prior to database lock and unblinding.

The number and percentage of patients with respiratory failure at any time from Baseline to Day 28 will be summarized by treatment. Associated 95% CI for the proportion of respiratory failure will be provided for each treatment group using Clopper-Pearson method. Patients without any post baseline oxygen requirement data recorded will be considered free of respiratory failure.

Changes in O₂ requirements which are considered to be respiratory failure will be flagged in the data listing.

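### When it fills in a missing PaO2/FiO2 ratio, the SAP prefers the blood-gas-page FiO2 to the FiO2 recorded with the saturation, so the derived ratio may combine SpO2 and FiO2 from different times (minor).

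*SAP*

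**What the plan says.** SAP 13.1.1.1 draws on two CRF pages. The O2 Saturation Readings page supplies a saturation and an FiO2; the PaO2/FiO2 page supplies a second FiO2. The estimated PaO2 "will be calculated based on the collected" saturation by way of a lookup table, and the ratio then follows as "Derived PaO₂/FiO₂ ratio = (Estimated PaO₂ / Collected FiO₂) x 100".

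For the denominator the order is explicit. An FiO2 on the PaO2/FiO2 "ratio CRF page, then this will be used for the collected" FiO2. Failing that, the FiO2 from the O2 "Saturation Readings CRF page will be used as the collected" FiO2. The derived PaO2/FiO2 "ratio will be used for imputation, if the collected" ratio is missing. Collected and imputed values together are then summarised, modelled and compared with a Wilcoxon test, and SAP 12.3 repeats this by country.

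On timing, Protocol 8.1.1 says of the blood-gas measurement that it "will be evaluated by blood gas analyzer at screening for eligibility determination, within 30 minutes before dosing on Day 1 as baseline". For Days 7 and 14 the window given is the half hour following the second dose. For oximetry, SAP 13.1.2 says only this: "Oxygen saturation will be measured daily via pulse oximetry". Protocol 8.1.2 says the same. The footnotes to the schedule of assessments give dose-related windows for vital signs and ECGs but none for oximetry.

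**The concern.** A saturation can be interpreted only at the inspired oxygen under which it was read. The rule takes the numerator from one record and, by preference, the denominator from another, although the first record has its own FiO2. It states no time window and does not say which saturation reading is used if there are several.

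The documents themselves expect oxygen support to change within a day. Exclusion criterion 1 allows periodic high-flow oxygen, and SAP 13.1.3 uses a dated and timed eCRF of changes in oxygen requirement to count fractional days on room air. If FiO2 changed between the two records, the imputed ratio describes neither moment. If the affected value is a Baseline, the error also enters that patient's later changes, percentage changes and model covariate within the derived-ratio analysis.

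**Working it through.** **Nothing to reproduce.** The plan states no error size for the derived ratio. The check applies the SAP's own table and formula to one saturation with two FiO2 values.

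**Inputs from the SAP (Table 13.1.1.1).** SpO2 90% maps to 60 mmHg, 94% to 73 mmHg and 96% to 86 mmHg. The printed formula is used with FiO2 in percent.

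**Assumed inputs.** The FiO2 pairs are illustrations; neither document reports any.

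**Formula.** With table value P and the two FiO2 values F1 and F2, the difference is 100 × P × (1/F1 − 1/F2). It is zero when F1 = F2.

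| SpO2 (table PaO2, mmHg) | FiO2 pair, % (assumed) | Ratios, mmHg | Difference, mmHg |
|---|---|---|---|
| any | equal | identical | 0 |
| 90% (60) | 40 vs 45 | 150.0 vs 133.3 | 16.7 |
| 96% (86) | 40 vs 45 | 215.0 vs 191.1 | 23.9 |
| 90% (60) | 40 vs 50 | 150.0 vs 120.0 | 30.0 |
| 96% (86) | 40 vs 50 | 215.0 vs 172.0 | 43.0 |
| 90% (60) | 21 vs 24 | 285.7 vs 250.0 | 35.7 |
| 96% (86) | 21 vs 24 | 409.5 vs 358.3 | 51.2 |
| 94% (73) | 28 vs 40 | 260.7 vs 182.5 | 78.2 |

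For example, 73/28 × 100 = 260.7 and 73/40 × 100 = 182.5. The sign depends on which page holds the larger FiO2.

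**When the rule operates.** Three conditions must all hold:
1. The collected ratio is missing.
2. The FiO2 on the PaO2/FiO2 page is present, for instance because only the PaO2 is absent.
3. That FiO2 differs from the one on the oximetry page.

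If the PaO2/FiO2 page has no FiO2, the fallback already takes both quantities from the oximetry page.

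**Effect on an arm mean.** Suppose k of 30 patients are each off by 40 mmHg in the same direction. The mean moves by k × 40/30: 1.3 mmHg for one patient, 4.0 for three and 8.0 for six. Errors in mixed directions would partly cancel.

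**The case against.** The strongest reply is that no mismatch has been shown. The schedule of assessments places the ratio and the oximetry on the same days (screening, Days 1, 7 and 14), and they could have been recorded together. SAP 13.1.3 shows that the oximetry eCRF carries dates and times, so matching may be feasible. The CRF is not among the documents. All of this stands: the documents allow different times but do not establish them.

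It is also fair that the consequence is contained. The analysis of the collected ratio in SAP 13.1.1 does not use derived values, the sample size rests on no power calculation, and p-values are offered only as an aid to interpretation. Nothing suggests that mismatches would differ between blinded arms.

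A reader might further infer that the multiplication by 100 is wrong, because the SAP calls the field a fraction and its definition of respiratory failure speaks of oxygen flow "with fraction of delivered oxygen" of at least 0.5. The documents do not support that. The printed formula is correct for FiO2 in percent, and the factor of 100 itself implies that format. The 0.5 belongs to a clinical definition and does not show how the CRF stores the value. A fractional entry would give a conspicuously impossible ratio, which the independent programming check and senior statistical review in SAP section 8 should catch.

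None of this supplies a reason for the order chosen. Where the two FiO2 values agree, the order is irrelevant. Where they differ, the rule discards the one recorded on the same page as the saturation.

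**Conclusion.** The point holds as a minor one. The stated precedence, with no time-matching rule, may combine SpO2 and FiO2 from different times. The error in an individual imputed ratio is zero if the two FiO2 values agree and can reach tens of mmHg for modest differences, as the table shows. Those sizes rest on assumed FiO2 pairs. How often all three conditions hold is unknown.

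Two stronger conclusions go too far. One is that values from different moments are in fact combined, which the documents leave open. The other is that the PaO2/FiO2 endpoint as a whole is compromised: only Tables 14.2.1.5.1 and 14.2.1.5.2 are exposed, and only for patients who meet all three conditions.

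**What to change.** Amend SAP 13.1.1.1 before the blind is broken:

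- Estimate PaO2 from the saturation reading nearest the scheduled PaO2/FiO2 assessment. Protocol 6.1 requires dose times to be recorded, so the scheduled window can be located even when no blood gas was taken.
- Divide by the FiO2 recorded on the O2 Saturation Readings page with that same reading.
- Only if that FiO2 is absent, use the one on the PaO2/FiO2 page, provided that the two records fall within a time window stated in the SAP.
- Otherwise leave the derived ratio missing.

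The cost is a few lines of SAP text and a small programming change, with no new data collection. The drawback is that a few derived values may become missing, including any fallback cases in which the PaO2/FiO2 page carries no time against which to check the window. Where the two FiO2 values agree, reversing the precedence leaves the result for a given reading unchanged.
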